10.5 Sample Size Considerations

For safety endpoints, the probability of observing at least 1 adverse event among 135, 155, or 310 subjects for each Quad-NIV formulation is > 90% if the true rate of such events is 1.7%, 1.5%, or 0.8%, respectively. With 135, 155, or 310 subjects for each treatment group, observing no adverse events of interest (eg, vaccine-related SAE) would represent an upper bound of the 1-sided 95% CI on the percentage of such event is 2.2%, 1.9%, or 1.0%, respectively.

This study has a single comparison of 2 treatment groups (Group B vs E) for the primary immunogenicity objective. No formal adjustment for multiple comparisons is planned for the 6 comparisons associated with the 6 strain-specific GMTs. The demonstration of the superiority of Quad-NIV (60 µg HA per A and B strain) co-formulated with 50 µg Matrix-M1 (Group B) as compared to Quad-NIV (60 µg HA per A and B strain) without adjuvant (Group E) requires simultaneous successes of all 6 tests (at least 2 strains meeting the strain-specific superiority criterion and the non-inferiority criterion for the remaining homologous strains). The non-inferiority for this trial will be carried out without a pre-specified margin. Non-inferiority is defined as the 2-sided 95% CI for the ratio of GMTs (Group B / Group E) containing 1.0 (ie, unadjusted 1-sided p-value ≥ 0.025 against the null hypothesis of H0: Ratio of GMT ≤ 1.0). The superiority is defined as the lower limit of the 2-sided 95% CI for the ratio of GMTs (Group B / Group E) > 1.0 (ie, unadjusted 1-sided p-value < 0.025 against the null hypothesis of H0: Ratio of GMT ≤ 1.0). For other immunogenicity analyses, the purpose is to determine a dose and formulation for the next study based on all available safety and immunogenicity results, including the primary objective analysis. Hence, any statistical analyses (ie, calculations of CIs and p-values) will also be performed without a multiplicity adjustment.

In a previous study using the Tri-NIV formulation (tNIV-E-101), the observed strain-specific standard deviations of \log_{10} HAI titers ranged from approximately 0.4 (B/Brisbane and A/Texas) to approximately 0.6 (A/Switzerland and A/Singapore). [Table 8](#) summarizes power, unadjusted for multiple comparisons, for the primary objective to demonstrate superiority for pair-wise comparisons of the 2 treatment groups. Power calculations also accounted for a 5% attrition rate for the per-protocol population (295 evaluable subjects per treatment group) which is the primary analysis population for all immunogenicity endpoints. For each strain, this study is designed to detect a 1.4-fold increase (40% increase) in GMTs with $\geq 84\%$ power. For 2 strains, this study is designed to detect a 1.5-fold increase (50% increase) in GMTs with $\geq 88\%$ power. For each strain, there will be 97.5% probability of demonstrating a non-inferior GMT for each comparison if 2 treatment groups have an equal GMT. Therefore, demonstrating a superiority against 2 strains with the true difference of 1.5-fold and a non-inferiority against 4 strains with the true difference of 1.0-fold, this study is designed to provide $\geq 80\%$ power.

Approved

Table 8: Power to Detect Percentage Increase in Ratio of GMTs Between 2 Treatment Groups

Per-Protocol N Group	Log ₁₀ SD	Fold Increase	Power
295	0.4	1.2	67%
		1.3	93%
		1.4	99%
		1.5	> 99%
		1.6	> 99%
		1.7	> 99%
		1.2	48%
	0.5	1.3	79%
		1.4	94%
		1.5	99%
		1.6	> 99%
		1.7	> 99%
		1.2	36%
	0.6	1.3	63%
		1.4	84%
		1.5	94%
		1.6	98%
		1.7	> 99%

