Primary Objectives	
 To describe the safety and tolerability of Quad-NIV at different doses (ie, 60 μg HA per A and B strain vs 60 μg HA per A strain and 90 μg HA per B strain) and formulations, without adjuvant or with 1 of 2 different doses of Matrix-M1 adjuvant (mixed in-clinic or co-formulated in advance of the trial), relative to 2 US-licensed comparators, Fluzone HD (Sanofi Pasteur) and Flublok Quadrivalent (Sanofi Pasteur, previously Protein Sciences Corp), in healthy adults ≥ 65 years of age. The safety profile will include solicited short-term reactogenicity; 28-day all adverse event (AE) profile; 1-year post-injection medically-attended adverse event (MAE), serious adverse event (SAE), and significant new medical condition (SNMC) profile; and selected pre- and post-vaccination clinical laboratory parameters. To demonstrate a Matrix-M1 adjuvant effect by demonstrating the immunogenic superiority of Quad-NIV (60 μg HA per A and B strain) co-formulated with 50 μg Matrix-M1 as compared to Quad-NIV (60 μg HA per A and B strain) without adjuvant. Immunogenic superiority will be demonstrated by excluding values ≤ 1.0 at the lower 95% confidence bound for the baseline-adjusted ratio of Day 28 post-vaccination HAI titers (ie, GMT adjuvant / GMT no adjuvant) for not less than 2 out of 6 influenza strains (ie, any 2 of 4 vaccine-homologous strains and/or 2 antigenically-drifted influenza strains), while no other strain(s) demonstrate a baseline-adjusted ratio of Day 28 post-immunization HAI titers which is significantly < 1.0.
Secondary Objectives	
 To compare the immunogenicity of Quad-NIV (60 μg HA per each A and B strain) with 50 μg of Matrix-M1 co-formulated prior to administration relative to a similar formulation mixed in-clinic and also to 2 US-licensed active comparators, Fluzone HD and Flublok Quadrivalent, in healthy adults ≥ 65 years of age, in terms of HAI antibody responses

Approved

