	
associated with the 6 strain-specific GMTs. The demonstration of the superiority of Quad-NIV (60 µg HA per A and B strain) co-formulated with 50 µg Matrix-M1 (Group B) as compared to Quad-NIV (60 µg HA per A and B strain) without adjuvant (Group E) requires simultaneous successes of all 6 tests (at least 2 strains meeting the strain-specific superiority criterion and the non-inferiority criterion for the remaining homologous strains). The non-inferiority for this trial will be carried out without a pre-specified margin. Non-inferiority is defined as the 2-sided 95% CI for the ratio of GMTs (Group B / Group E) containing 1.0 (ie, unadjusted 1-sided p-value ≥ 0.025 against the null hypothesis of H_0: Ratio of $GMT \leq 1.0$). The superiority is defined as the lower limit of the 2-sided 95% CI for the ratio of GMTs (Group B / Group E) > 1.0 (ie, unadjusted 1-sided p-value < 0.025 against the null hypothesis of H_0: Ratio of $GMT \leq 1.0$). For other immunogenicity analyses, the purpose is to determine a dose and formulation for the next study based on all available safety and immunogenicity results, including the primary objective analysis. Hence, any statistical analyses (ie, calculations of CIs and p-values) will also be performed without a multiplicity adjustment.
 
In a previous study using the Tri-NIV formulation (tNIV-E-101), the observed strain-specific standard deviations of \log_{10} HAI titers ranged from approximately 0.4 (B/Brisbane and A/Texas) to approximately 0.6 (A/Switzerland and A/Singapore). The table below summarizes power, unadjusted for multiple comparisons, for the primary objective to demonstrate superiority for pair-wise comparisons of 2 treatment groups. Power calculations also accounted for a 5% attrition rate for the per-protocol population (295 evaluable subjects per treatment group) which is the primary analysis population for all immunogenicity endpoints. For each strain, this study is designed to detect a 1.4-fold increase (40% increase) in GMTs with $\geq 84\%$ power. For 2 strains, this study is designed to detect a 1.5-fold increase (50% increase) in GMTs with $\geq 88\%$ power. For each strain, there will be 97.5% probability of demonstrating a non-inferior GMT for each comparison if 2 treatment groups have an equal GMT. Therefore, demonstrating a superiority against 2 strains with the true difference of 1.5-fold and a non-inferiority against 4 strains with the true difference of 1.0-fold, this study is designed to provide $\geq 80\%$ power.
 
Power to Detect % Increase in Ratio of GMTs Between 2 Treatment Groups
			

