## 9 SAMPLE SIZE CONSIDERATIONS

For safety endpoints, the probability of observing at least 1 adverse event among 135, 155, or 310 subjects for each Quad-NIV formulation is > 90% if the true rate of such events is 1.7%, 1.5%, or 0.8%, respectively. With 135, 155, or 310 subjects for each treatment group, observing no adverse events of interest (eg, vaccine-related SAE) would represent an upper bound of the 1-sided 95% CI on the percentage of such event is 2.2%, 1.9%, or 1.0%, respectively.

This study has a single comparison of 2 treatment groups (Group B vs E) for the primary immunogenicity objective. No formal adjustment for multiple comparisons is planned for the 6 comparisons associated with the 6 strain-specific GMTs. The demonstration of the superiority of Quad-NIV (60 µg HA per A and B strain) co-formulated with 50 µg Matrix-M1 (Group B) as compared to Quad-NIV (60 µg HA per A and B strain) without adjuvant (Group E) requires simultaneous successes of all 6 tests (at least 2 strains meeting the strain-specific superiority criterion and the non-inferiority criterion for the remaining 4 strains). The non-inferiority for this trial will be carried out without a pre-specified margin. Non-inferiority is defined as the 2-sided 95% CI for the ratio of GMTs (Group B / Group E) containing 1.0 (ie, unadjusted 1-sided p-value  $\geq 0.025$  against the null hypothesis of H0: Ratio of GMT  $\leq 1.0$ ). The superiority is defined as the lower limit of the 2-sided 95% CI for the ratio of GMTs (Group B / Group E)  $> 1.0$  (ie, unadjusted 1-sided p-value  $< 0.025$  against the null hypothesis of H0: Ratio of GMT  $\leq 1.0$ ). For other immunogenicity analyses, the purpose is to determine a dose and formulation for the next study based on all available safety and immunogenicity results, including the primary objective analysis. Hence, any statistical analyses (ie, calculations of CIs and p-values) will also be performed without a multiplicity adjustment.

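### The written success rule for Group B vs Group E explains non-inferiority with a p-value condition that points the wrong way, and limits it to homologous strains against the stated objective

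*Protocol*

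**What the plan says.** The primary immunogenicity comparison is Group B (co-formulated with 50 µg Matrix-M1) against Group E (no adjuvant) on six strains, four homologous and two drifted.

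- **The objective.** The synopsis (objectives and statistical methods), Protocol 2.1 and 10.4.1.2, and SAP 2.1.1 require superiority on at least two strains, "while no other strain(s) demonstrate a baseline-adjusted ratio of Day 28 post-immunization HAI titers which is significantly" below 1.0. No strain is exempt.
- **The sample size text.** Protocol 10.5, its synopsis counterpart and SAP 9 define non-inferiority, without a margin, as the interval "containing 1.0 (ie, unadjusted 1-sided p-value ≥ 0.025 against the null hypothesis of H0: Ratio of GMT ≤ 1.0". The next sentence defines superiority as a one-sided p below 0.025 against that same null.
- **Scope in the protocol.** Protocol 10.5 and the synopsis say that the demonstration "requires simultaneous successes of all 6 tests", but in the same sentence describe the second part as "the non-inferiority criterion for the remaining homologous strains".
- **Scope elsewhere.** SAP 9 says "the non-inferiority criterion for the remaining 4 strains". The power statement in Protocol 10.5 assumes "a non-inferiority against 4 strains with the true difference of 1.0-fold".
- **Stated probability.** Protocol 10.5 adds that "there will be 97.5% probability of demonstrating a non-inferior GMT for each comparison if 2 treatment groups have an equal GMT".

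The synopsis methods text and Protocol 10.4.1.2 give the objective's rule and then send the reader to the sample size section for the details. SAP 7.1 names the comparison and its model but neither restates the pass/fail rule nor cites SAP 2.1.1.

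**The concern.** There are two separate faults. First, the p-value explanation tests against the null that B is no better than E, when a guard against harm has to test against the null that B is no worse. As worded, any strain that is not superior passes, including one whose whole interval lies below 1.0, so the condition can never fail. Second, the word 'homologous' would leave a significantly worse drifted strain without effect on the verdict, although the objective says such a strain blocks success.

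B vs E is the trial's only confirmatory comparison, and drifted strains are central to its rationale. A confirmatory rule should have one reading, and both faults sit in the section to which the correct statements refer for details.

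**Working it through.** **Inputs.** 295 evaluable per arm (310 less 5%), log10 SD 0.4 to 0.6, two strains at 1.5-fold and four at 1.0 (all Protocol 10.5); two-sample t-test (SAP 11). Two-sided 5%, df 588, critical t 1.964, SE = SD × √(2/295). Strains are taken as independent, as the plan's product implies.

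**1. The plan's own figure.** At SD 0.6 and 1.5-fold, power per strain is 0.945 (Table 8: 94%). Two strains: 0.945² = 0.893 (stated at least 88%; 0.94² = 0.884 from the rounded cell). Whole rule: 0.945² × 0.975⁴ = 0.807 (stated at least 80%). It reproduces.

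**2. Explanation against definition.** One-sided p ≥ 0.025 against ratio ≤ 1.0 is the same as lower limit ≤ 1.0; the upper limit is unconstrained. Example with an assumed observed ratio of 0.80 and SD 0.5: SE = 0.0412, interval 10^(log10 0.80 ± 1.964 × 0.0412) = 0.66 to 0.96, one-sided p = 0.99. That strain meets the explanation but fails both the interval definition and the objective.

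**3. What the 97.5% settles.** At equal GMTs, the upper limit is at least 1.0 with probability 0.975, the explanation is met with probability 0.975, and the interval contains 1.0 with probability 0.95. The stated 97.5% therefore does not separate the objective's rule from the faulty explanation. It does differ from a literal reading of 'contains 1.0'.

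**4. Scope, in the plan's scenario at SD 0.6.** Let p = 0.945 and q = 1 − p = 0.055 for the two strains at 1.5-fold (q² = 0.00302, 2pq = 0.1039). Each strain at 1.0 is superior with probability 0.025, neither with 0.95, and worse with 0.025. A strain truly at 1.5-fold is significantly worse with negligible probability. Success = P(no covered strain worse) minus the cases with 0 or 1 superior strain.

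- Objective, all strains covered: 0.975⁴ − q² × 0.95⁴ − 2pq × 0.95⁴ − q² × 4 × 0.025 × 0.95³ = 0.9037 − 0.0025 − 0.0846 − 0.0003 = **0.816**.
- Homologous only, both superior strains homologous: 0.975² − q² × 0.95² × 0.975² − 2pq × 0.95² × 0.975² − q² × (2 × 0.025 × 0.95 × 0.975² + 0.95² × 2 × 0.025 × 0.975) = 0.9506 − 0.0026 − 0.0891 − 0.0003 = **0.859**.

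The gap is 85.9 − 81.6 = 4.3 points. If both truly superior strains were the drifted ones, the two readings would coincide at 81.6% in this scenario. The objective's figure slightly exceeds the 80.7% product because a strain at 1.0 can also come out superior.

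**5. Where a strain counts as significantly worse.** Observed ratio below 10^(−1.964 × SD × √(2/295)): 0.86, 0.83 and 0.80 at SD 0.4, 0.5 and 0.6. These use the unadjusted SD. The planned ANCOVA adjusts for baseline, which moves them closer to 1.0. With an assumed baseline to Day 28 correlation r of 0.5 to 0.7, replacing SD by SD × √(1 − r²) gives about 0.88 to 0.90, 0.85 to 0.88 and 0.82 to 0.85. The documents give no correlation.

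**6. Stress case, assumed and not in the documents.** Two homologous strains at 1.5, one drifted strain truly at 0.67, three at 1.0, SD 0.6. Enumerating all 3⁶ strain outcomes gives success of 5.0% under the objective, 85.6% homologous-only and 90.1% under the explanation alone. Over SD 0.4 to 0.6 and a drifted ratio of 0.67 to 0.80, the ranges are 0.04% to 41.8%, 85.6% to 95.0% and 90.1% to 99.9%.

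**The case against.** The strongest reply is that the rule is not in real doubt. It is stated correctly in five places. The SAP's own scope is consistent, since SAP 2.1.1 and SAP 9 both cover every remaining strain. SAP 7.1 outputs a two-sided 95% interval and SAP 12 makes all analyses two-tailed, so nobody is likely to apply the p-value explanation on its own. The requirement for all 6 tests, in the same sentence, counters the homologous-only reading. All of this stands, and it lowers the severity. It does not make the text right: reading the interval does not say which strains count, and no passage says which wording governs.

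A reader might go further in three ways that the documents do not support.

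- *That the plan lets inferior strains through.* SAP 9's interval definition, applied to every strain not shown superior, is equivalent to the objective. Only the explanation and one word depart from it.
- *That power falls to 0.945² × 0.95⁴ = 72.7% because an interval contains 1.0 only 95% of the time at equality.* That would count an additional superior strain as a failure, and the plan asks for at least two superior strains, not exactly two.
- *That the SAP changed the rule without recording it, since SAP 13 lists no change.* SAP 9's four strains agree with the protocol's objective, analysis text and power statement, so there is no clear change to record.

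**Conclusion.** The concern holds as a should-fix error in how the success rule is written. Two points are certain from the text alone: the p-value explanation has its null the wrong way round in all three places, and 'homologous' conflicts with its own sentence, the power statement, SAP 9 and the objective.

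The size is modest on the plan's own assumptions: 81.6% against 85.9%, given SD 0.6, independent strains, an unadjusted two-sample t-test and both superior strains homologous. A reader might infer from the stress case that the choice of wording moves success from 5% to 86% or 90%. That gap arises only if a drifted strain is assumed truly worse with adjuvant, which no passage anticipates. It shows that the readings can diverge, not how likely that is. The stated power of at least 80% and the sample size are unaffected.

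**What to change.** In Protocol 10.5, the synopsis and SAP 9, state the rule once in the same words and cross-refer to it from SAP 7.1: at least 2 of the 6 strains have a lower two-sided 95% limit for the B/E ratio above 1.0, and every other strain, homologous or drifted, has an upper two-sided 95% limit of at least 1.0 (one-sided p ≥ 0.025 against the null that the ratio is ≥ 1.0). Delete the present p-value explanation and the word 'homologous'. The upper-limit wording matches both the objective and the stated 97.5%. Renaming the condition 'no significant inferiority', since no margin is set, is optional.

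The cost is a wording amendment to the protocol, which Protocol 9.5 requires to be signed and submitted to the IRB, plus a SAP edit. If an amendment is no longer practical, a note in the SAP or study report that the rule in Protocol 2.1 and SAP 2.1.1 governs is enough. SAP 12 and 14.1 already carry changes made after unblinding, so the note should say plainly that this is the pre-stated objective and not a new criterion. No data, sample size or power figure changes.

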10.6 Plan for Statistical Summaries and Analyses

10.6.1 Day 28 Unblinded Data Review

An unblinded review will be conducted of all available immunogenicity and safety data (inclusive of clinical laboratory safety assessments) upon completion of Day 28 visits for all subjects and at least the completion of HAI data concerning all four vaccine-homologous virus strains and at least 2 antigenically-drifted influenza strains at Days 0 and 28. For the review, treatment codes will only be unblinded after the data are deemed ready for the analysis after all subjects have completed the Day 28 visit and the data are monitored. The determination of the readiness will be based on the blinded review of outstanding queries of critical data points. Given the time-consuming nature of the microneutralization and cellular response assays, these data may be presented only in the final CSR (see Section 10.6.2).

In order to execute this review, a select group of trial staff will be unblinded at the CRO and at Novavax. All personnel unblinded to the trial data will be documented. No individual unblinded at a subject treatment level will be involved in follow-up safety monitoring. Specifically, personnel at the clinical trial site including, investigators and trial staff, research site, immunology laboratory, and trial subjects will remain blinded to treatment assignments until the end of trial (ie, Day 364).

Approved

Nanoparticle Influenza Vaccine, Quadrivalent
Novavax, Inc. Confidential
Version 3.0 – 21 August 2018

qNIV-E-201 Protocol
Page 75

Since trial procedures and monitoring practices will not change following the review and the trial will not be terminated prematurely on the basis of these data, no decision cut points or stopping rules will be stipulated.

Immunogenicity and safety analyses from the unblinded review may be presented in an abbreviated unblinded clinical study report (CSR) drafted by the Sponsor that may be submitted to regulatory authorities as needed.

10.6.2 Final Clinical Study Report

The final CSR will present the balance of all safety and immunogenicity (if any) data through Day 364 (the scheduled end of trial). The database will be locked and the final CSR prepared, when all of the above data have been entered, reviewed, and all queries related to the data have been addressed. Any decisions to deviate from the planned analyses will be described in detail in the final CSR.

10.7 Computer Methods

Statistical analyses will be performed using SAS® version 9.3 or greater under a Windows operating system.

Approved

11 TRIAL LEGAL AND ETHICAL REQUIREMENTS

11.1 Compliance with Regulatory Requirements

This trial will be conducted in accordance with the protocol, the Declaration of Helsinki (amended Fortaleza, Brazil, 2013), International Conference on Harmonisation (ICH) GCP Guidelines, and the US FDA regulatory requirements.

11.2 Ethics Committee

This trial will be conducted under the auspices of a properly-constituted IRB, as defined by US regulatory requirements, and in accordance with the Declaration of Helsinki (amended Fortaleza, Brazil, 2013). This committee will review and approve all aspects of the trial, including the protocol and ICF to be used, any and all advertising or informational materials, and any modifications made to the protocol and ICF, prior to, or during the trial. Prior to initiation of clinical activity, investigators will provide Novavax with a copy of the communication from the IRB indicating approval of the protocol and ICF. In the event that a central IRB is used, Novavax will provide copies of correspondence to the investigators. All changes to the protocol or ICF must be reviewed and approved prior to implementation, except where necessary to eliminate apparent immediate hazards to human subjects.

If applicable, the investigators will be responsible for obtaining annual IRB renewal throughout the duration of the trial. Copies of the investigators' annual report to the IRB and copies of the IRB continuance of approval must be furnished to Novavax.

11.3 Informed Consent

The investigators or designated site trial staff members will be responsible for obtaining written informed consent (and any applicable local or state regulatory documentation), signed and dated by each subject, prior to his/her participation in the trial. Informed consent will be obtained from a subject after a full explanation of the purpose of the trial, the risks and discomforts involved, potential benefits, etc, have been provided by the investigators, both verbally and in writing. The original signed copy of the ICF must be maintained in the institution's records and will be subject to inspection by a representative of Novavax and/or regulatory agencies. The subject will also be given a copy of the signed consent form.

